## 8 Data Recording and Management

### 8.1 Investigator Data Recording

Detailed records of all eligible subjects, including laboratory results.

Two nuclear medicine physicians ( $\geq 5$  years' experience) independently interpret imaging; discrepancies resolved by a senior consultant.

Original data signed and dated by the investigator.

All adverse events (AEs) documented; serious adverse events (SAEs) reported per protocol.

---

## 9 Expected Timeline

Recruitment period: 36 months

Follow-up: Ends upon completion of 18F-Octreotide PET/CT and pathological confirmation.

---

## 10 Adverse Event Assessment and Reporting

### 10.1 Definition

Any untoward medical occurrence related to imaging/radiopharmaceuticals during/after the study, including symptoms, signs, or lab abnormalities.

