#### 5.3.3 Criteria and Procedures for Subject Withdrawal:

Subjects not meeting inclusion criteria (verified via medical history/electronic records) will be excluded. Subjects may withdraw during the procedure due to hypoglycemia, tremor, pain, or severe abdominal discomfort.

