### 5.4 Study Endpoints:

Study completion is defined as completion of multimodal imaging and acquisition of pathological results.

---

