## 6. Research Procedures and Protocols

### 6.1 Ethics and Informed Consent

- The study commences after ethics committee (EC) approval. Protocol amendments require re-approval.
- EC approval (including consent forms) must be documented with version/date.

- Written informed consent is mandatory before enrollment.

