## 6.2 Subject Screening

- Consent is obtained after explaining risks/benefits. Subjects receive time to consider participation.
- Baseline data (general exams, labs, history from within 1 week pre-consent) are collected. Adverse events/concomitant medications are recorded post-consent.

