## 10.3 Documentation of AEs

Use standardized medical terminology.

Include:

Start/end dates

Severity

Causality assessment

Action taken

Outcome

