## 10.5 AE Follow-up

All AEs followed until resolution.

---

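### The AE definition in 10.1 admits only imaging- or tracer-related events, so unrelated judgements go unrecorded; separately, 6.4 and 6.8 give opposite fasting rules

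*Protocol*

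**What the plan says.** Section 10.1 of the protocol holds its only definition of an AE: "Any untoward medical occurrence related to imaging/radiopharmaceuticals during/after the study, including symptoms, signs, or lab abnormalities". Section 10.3 then lists what to document for an AE: start and end dates, severity, "Causality assessment", action taken and outcome.

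Three other sections rely on the term without defining it. Section 6.2: "Adverse events/concomitant medications are recorded post-consent". Section 8.1: "All adverse events (AEs) documented; serious adverse events (SAEs) reported per protocol". Section 10.5: "All AEs followed until resolution".

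Two sections bear on which events may arise. Section 5.3.3: "Subjects may withdraw during the procedure due to hypoglycemia, tremor, pain, or severe abdominal discomfort". Section 5.4: "Study completion is defined as completion of multimodal imaging and acquisition of pathological results", so a subject completes the study only after a biopsy or operation has supplied pathology. Section 9 ends follow-up at PET/CT plus pathological confirmation.

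On conduct, 6.4 states that fasting is not needed. The procedure flow in 6.8 makes a fast of at least 4 h part of preparation (step 2) and puts history and consent at step 3, ahead of injection at step 4. Section 6.1: "Written informed consent is mandatory before enrollment". Section 6.2 takes consent at screening, with time to consider.

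**The concern.** An AE record normally takes in every untoward event and leaves its cause to a separate, reviewable assessment. Here the order is reversed: the person at the bedside must decide that an event is related before it qualifies as an AE. An event judged unrelated leaves no AE record, so nobody can later check that judgement or see a pattern across subjects. The safety assessment mentioned in 5.3.4 would then hold only events already presumed related.

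The fasting rules are a separate matter of conduct. Both apply to the same scan, and staff cannot follow both. The place of consent in the 6.8 flow is a smaller matter of the same kind.

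**Working it through.** No arithmetic applies beyond counting, so the check sets the sections side by side.

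**Step 1: what 10.1 lets in.** Four kinds of event, as 10.1 is written:

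- Rash attributed to the tracer: an AE, and 10.3 and 10.5 apply.
- Symptom during the visit attributed to the tumour: not an AE.
- Complication attributed to the biopsy or operation that supplies the pathology: not an AE, although it can fall inside the follow-up period of section 9.
- Event during preparation: an AE only if imaging is read to include preparation. That reading does not bring in the second and third kinds.

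For an event that fails 10.1, 0 of the 5 items in 10.3 are required, and causality is one of those five. Follow-up under 10.5 is not required either.

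**Step 2: whether another section repairs this.** Sections 8.1 and 10.5 both speak of all AEs, but all is counted within the 10.1 definition. Neither widens it.

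**Step 3: 10.1 beside 6.2.** Section 6.2 starts AE recording at consent. Before the first study scan or injection, little or nothing can be related to study imaging or tracer. Under 10.1, that early recording therefore has almost nothing to capture. Section 6.2 sets a start time and does not define an AE, so the mismatch is implied.

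**Step 4: fasting.** Section 6.4 gives no required fast; section 6.8 gives at least 4 h. This is a direct contradiction.

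**Step 5: order of consent.** In 6.8, 2 of 6 steps (registration, preparation) come before consent. In section 6, consent (6.2) comes before history (6.3) and preparation (6.4). The orders differ, but every section puts consent before injection.

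**The case against.** The strongest reply on AEs is that 10.1 and 10.3 can coexist. Causality may be graded by degree, or split between tracer and scan, among the events that 10.1 admits, and a narrow scope might be a deliberate choice for a single-dose diagnostic tracer. The first part stands: this is not a strict contradiction. It does not answer the main point, because an unrelated verdict still removes the event before the causality item is reached.

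A reader might infer that 6.2 contradicts 10.1 outright. It does not: a start date earlier than the first possible event is redundant rather than conflicting. Nor can a length be put on that early period, since the protocol gives no interval from consent to scan.

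A reader might link the fast in 6.8 to the hypoglycemia in 5.3.3. The protocol gives no cause for those symptoms, so no such link is claimed.

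A reader might also take the 6.8 flow as evidence that subjects are prepared without consent. The text does not support that. Section 6.1 requires consent before enrollment, not before every procedure; 6.2 takes it at screening; and step 3 of 6.8 may be a scan-day check.

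Finally, one might assume that the synopsis termination criterion on serious adverse events (SAEs) already means related SAEs only. The protocol has no SAE definition to show that SAEs inherit the condition in 10.1, and narrowing the criterion on that assumption could weaken a stopping safeguard.

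**Conclusion.** Two points hold firmly. First, 10.1 makes relatedness a condition of being an AE, so an unrelated judgement leaves no required record, causality assessment or follow-up. Second, 6.4 and 6.8 cannot both be followed on fasting. The mismatch with 6.2 is real but only implied, and the consent order in 6.8 is a minor correction.

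The AE definition applies to all 152 planned subjects. How many events it would exclude cannot be stated, because the protocol gives no event rate. The conclusion assumes only that 10.1 is applied as written. It concerns safety capture and conduct. The sample size and the diagnostic accuracy estimates do not depend on it. The sponsor should make the change, but it does not undermine the study's main results.

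**What to change.** 1. **Section 10.1.** Define an AE as any untoward occurrence from consent until the end of follow-up in section 9 (PET/CT and pathological confirmation), whatever its suspected cause. Keep later events that are suspected to be related to imaging or tracer. Leave cause to the causality item in 10.3.
2. **Sections 6.4 and 6.8.** State one fasting rule in both. Either delete the fast from 6.8 or, if it is needed for the contrast-enhanced CT/MR in 2.2, correct 6.4.
3. **Section 6.8.** Place study consent before preparation.
4. **Synopsis.** Decide explicitly whether the termination criterion on SAEs means related SAEs or all SAEs, because a wider AE definition makes the question unavoidable.

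The cost is one amendment with the ethics re-approval that 6.1 requires. Staff will record more AEs, including some later judged unrelated, and follow them under 10.5. Unrelated SAEs, such as surgical complications, will need the 24-hour written reports of 10.4. The telephone follow-up of external patients, now meant for pathology results, must also ask about AEs. Sample size, imaging and analysis do not change.

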## 10.2 Major Adverse Events

PET/CT risks: Potential radiation exposure.

F-Octreotide risks: Rare mild reactions (rash, pruritus); severe reactions (shock) not reported in literature.

## 10.3 Documentation of AEs

Use standardized medical terminology.

Include:

Start/end dates

Severity

Causality assessment

Action taken

Outcome

## 10.4 Reporting of SAEs

Immediate actions taken.

Written reports submitted within 24 hours to:

Institutional Ethics Committee

Provincial regulatory authorities

Contact:

Affiliated Hospital 1, Zhejiang University School of Medicine

[name]: [name]

[name]: [name]

## 10.5 AE Follow-up

All AEs followed until resolution.

---

## 11 Quality Control (QC) & Assurance (QA)

### 11.1 Laboratory QC

18F-Octreotide prepared per Chinese Pharmacopoeia 2015.

Batch testing: pH, specific activity, radiochemical/radionuclide purity, endotoxin, sterility.

Reports signed and dated.

### 11.2–11.4 Staff & Procedures

Investigators: Certified, GCP-trained, and experienced.

Pre-study training on protocols.

QA ensures compliance with Good Practice for Radioactive Pharmaceuticals.

---

## 12–14 Data Confidentiality & Storage

Confidentiality: Subject identities protected; data anonymized (ID codes only).

Storage: Original records retained for 10 years post-study.

---

## 15 Study Termination & Reporting

Summary report prepared by lead unit and submitted to regulatory authorities.

Results may be published or used for regulatory submissions.

---

